9.7. Blood sampling

9.7.1. On admission/baseline

On study admission, immediately before drug administration, blood will be collected for the following:

- Repeat parasite count (thick and thin films). If it is found subsequently that this parasitaemia no longer meets the inclusion criterion for parasitaemia the patient will be kept in the study.
- Dry blood blots (200 microlitres, 4 spots collected on chromatography papers) for parasite and host genotyping (see section 14.3 for details on parasite genotyping and section 9.7.6 for details on host genotyping)
- Full blood count OR WBC differential, HCT, Hb (0.5 mL EDTA-anticoagulated)
- Parasite DNA and RNA measurements (packed cells from up to 5 ml for child, 10 mL from subjects ≥ 12 years in Gambia, Rwanda only) EDTA-anticoagulated blood; an aliquot of plasma will be stored for immunological assessments.
- *Ex vivo/in vitro* parasite cultivation for drug sensitivity and transcriptomic assays (2 ml child, heparinised blood, some sites; 3 mL from subjects ≥ 12 years in Gambia, Rwanda only).
- Baseline biochemistry assessments including bilirubin, ALT, AST, Alkaline Phosphatase and creatinine levels (1 mL heparin)
- Baseline Pharmacological measurement (1 mL heparin)

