9.10. Blood volumes

The blood volumes for the protocol mandated tests are detailed in the study schedule (Appendix 1) and will vary slightly between sites depending on whether sites can perform all of the tests of this protocol e.g. not all sites will be able to do the full blood count, store the plasma PK samples or do the *ex vivo* parasite culture. Also, it is likely that only a minority of subjects will develop a recurrent parasitaemia and be requested to give further blood samples.

Concerning blood volumes, an age of 12 years and older will be referred to as 'adult', an age of less than 12 years will be referred to as 'child'.

Maximum blood volumes are presented below for 63 days of follow up. The maximum blood volume is the total amount taken if the subjects remained in hospital for 3 days, had all blood samples taken and where part of the pharmacokinetic as well as other subsets (like qPCR validation and sampling for gametocyte genetics) and had one recurrent parasitaemia and/or unscheduled visit during follow up. The maximum blood volume will be approximately **48.5 ml (66.5 mL** in subjects ≥ 12 years in Gambia, Rwanda only), which is less than 10% of total blood volume generally recommended as a maximum volume to be taken over 8 weeks.. At the Niger site ONLY, where an additional 1 mL sample will be collected within a random time window between D0 & D7, the maximum blood volume will be approximately **49.5 mL**.

The maximum blood volume that will be drawn in children below the age of 12 is **17.5 ml** in the first 24 hours of the study. This is below the 3 ml/kg in the first 24 hours as recommended only if

the subjects are ≥ 6 kg [25]. Accordingly, samples collected from children of <6 kg will only be those which are specifically required for the efficacy, safety and tolerability assessments, viz., blood smears, dried blood spots, venous samples for clinical biochemistry, haematology and PK samples.

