12.1.2. Grading of laboratory abnormalities

Basic biochemical assessments of markers related to hepatic and renal toxicity will be performed on day 0 (baseline) day 3, day 7 and 28.

In addition haemoglobin, platelet counts, white blood cell counts and white blood cell differentiation will be obtained at day 0, day 3, day 7 and day 28.

If found to be abnormal the values will be graded according to the CTCAE table and followed up until resolved or deemed to be permanent.

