19.4.2. Risks of amodiaquine

The main side-effects of amodiaquine are nausea, vomiting and fatigue which are mild to moderate in nature. When the drug was used for prophylaxis, rare adverse reactions of agranulocytosis and hepatotoxicity were observed.

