#### 2.1.3. Secondary objectives and endpoints

- To compare the safety and tolerability of ACTs and TACTs within and across sites and regions, including comparisons of 'non-matching' ACTs vs TACTs (AL+Placebo versus ASMQ+PPQ, ASMQ+Placebo versus AL+AQ).
  - Incidence of adverse events and serious adverse events within the first 42 days including markers of hepatic, renal or bone marrow toxicity; cardiotoxicity, in particular QT or QTc-interval above 500 ms at timepoint H4 and H52/H64 and between these time points; change from baseline in haemoglobin at days 3, 7, 28, stratified for G6PD status/genotype; proportion of subjects requiring retreatment due to vomiting within 1 hour after administration of the study drugs; proportion of subjects that reports completing a full course of observed TACT or ACT without withdrawal of consent or exclusion from study because of drug related serious adverse event
  - Changes in the electrocardiogram (such as prolongation of the QTc-interval) in patients treated with TACT versus standard ACT
- To compare additional measures of treatment efficacy between treatment arms, including the 63-day ACPR, the post-treatment prophylactic effect of ACTs and TACTs defined as the 42-day & 63-day PCR uncorrected ACPR, gametocyte carriage, parasite clearance rates and fever clearance.

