### **3.4 Safety and tolerability of ACTs and TACTs within and across sites and regions, including comparisons of 'non-matching' ACTs vs TACTs (AL+Placebo versus ASMQ+PPQ, ASMQ+Placebo versus AL+AQ).**

Safety analyses will be based on the whole population that get administered the study drug. That is, the safety and tolerability data will be pooled from all the sites that received the same antimalarial treatment. Safety and tolerability of TACTs versus ACTs will be assessed by comparing the frequency (%) of adverse events and serious adverse events, with particular attention to abdominal pain, appetite perturbation, biochemical markers of hepatic and renal toxicity and QT interval prolongation, using the Fisher's exact test. Safety data will be presented in tabular and/or graphical format and summarized descriptively. Any clinically relevant abnormalities or values of potential clinically concern will be described. Patients will be analysed following the intention to treat analysis. All adverse event summaries will refer to treatment emergent adverse events, i.e. adverse events that newly started or increased in intensity after the study drug administration. Adverse events will be graded according to Division of AIDS table for grading the severity of ADULT AND PEDIATRIC adverse Events Version 2.0, November, 2014. The relevant DAIDS table will be appended to this document. The safety and tolerability summaries will be presented in tables 6.

The frequency and proportion of subjects that reports completing a full course of observed TACT or ACT without withdrawal of consent or exclusion from study because of drug related serious adverse events will be summarized within and across sites and regions. The 95% confidence intervals will be reported for the proportions. The proportions will be compared between matching drugs. The analyses will be summarised in table 7.

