## STATISTICAL ANALYSIS PLAN

Sleeping disturbance	X/XX (X.X)							
Laboratory abnormalities, n/N (%)	X/XX (X.X)							
Creatinine	X/XX (X.X)							
Total bilirubine	X/XX (X.X)							
Alkaline phosphatase	X/XX (X.X)							
Alanyl transfarase (ALT)	X/XX (X.X)							
Aspartate transfarase (AST)	X/XX (X.X)							

QTc: QT corrected using Bazett's formula. Adverse event grading: grade 1: mild; grade 2: moderate; grade 3: severe; grade 4: potentially life-threatening

Incidence of QTc abnormalities (>500 milliseconds) and bradycardia is defined as a subjects experience these abnormalities at one or more timepoints.

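### Bone-marrow toxicity is in the secondary safety endpoint, but the SAP plans no comparison of white cells, neutrophils or platelets, and the protocol is inconsistent about where those counts are measured

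*SAP*

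**What the plan says.** **Endpoint.** SAP 2.1.3, matching Protocol 5.2, defines the safety endpoint as "Incidence of adverse events and serious adverse events within the first 42 days including markers of hepatic, renal or bone marrow toxicity".

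**Analysis.** SAP 3.4 compares the frequency of adverse events and serious adverse events by Fisher's exact test, "with particular attention to abdominal pain, appetite perturbation, biochemical markers of hepatic and renal toxicity and QT interval prolongation". Protocol 15.2.4 singles out the same items. The laboratory block of SAP Table 6 has rows for creatinine, total bilirubin, alkaline phosphatase, ALT and AST. A separate row covers haemoglobin change at days 3, 7 and 28, stratified by G6PD status. The table's footnote adds: "Incidence of QTc abnormalities (>500 milliseconds) and bradycardia is defined as a subjects experience these abnormalities at one or more timepoints".

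**Measurement.** Protocol 12.1.2 says that "haemoglobin, platelet counts, white blood cell counts and white blood cell differentiation will be obtained at day 0, day 3, day 7 and day 28". Section 7 likewise lists platelets and absolute and differential white-cell counts among the safety assessments. The sampling list in 9.7.1 reads "Full blood count OR WBC differential, HCT, Hb (0.5 mL EDTA-anticoagulated", and 9.7.2 and 9.7.3 allow the same choice on days 3, 7 and 28. Section 9.10 says that "not all sites will be able to do the full blood count".

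**Known risk.** Protocol 19.4.2 states that, when amodiaquine was used for prophylaxis, "rare adverse reactions of agranulocytosis and hepatotoxicity were observed". Section 3.1 reports a higher incidence of bradycardia with amodiaquine in both adults and children.

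**The concern.** The endpoint names three organ systems, and the analysis text carries two of them forward. The third, bone marrow, bears on a harm that the protocol itself names for amodiaquine, the drug that distinguishes AL+AQ from AL plus placebo. An analyst who fills in the table shells as written would produce no comparison of white cells, neutrophils or platelets between matching arms.

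Bradycardia is a smaller case of the same kind. The SAP defines how its incidence is counted and then gives it nowhere to appear, although the protocol links it to amodiaquine.

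The measurement text adds a second problem. Even with the rows added, a reader could not tell from the protocol how many subjects have a platelet count or an absolute neutrophil count. An absence of marrow events cannot be interpreted without the number tested.

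**Working it through.** **1. Sampling schedule.** Day 0 is in Protocol 9.7.1, day 3 in 9.7.2, and days 7 and 28 in 9.7.3, each at 0.5 mL. 4 x 0.5 mL = 2 mL, which is the total Appendix 1 gives for the full blood count. The four occasions are therefore consistent; only what is measured on them is not.

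**2. From endpoint to table.**

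| Item | Singled out in SAP 3.4 | Row in Table 6 |
|---|---|---|
| Hepatic markers | yes | bilirubin, alkaline phosphatase, ALT, AST |
| Renal marker | yes | creatinine |
| QTc above 500 ms | yes (QT prolongation) | yes |
| Haemoglobin | no | change at days 3, 7, 28 |
| Total white cells, neutrophils | no | none |
| Platelets | no | none |
| Bradycardia | no | none, although the footnote defines it |

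No other SAP section fills the gap. Section 3.11 covers haematocrit and defers its detailed plan.

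**3. What is measured, by protocol section.**

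| Section | Content |
|---|---|
| 7 | haemoglobin, platelets, absolute and differential white cells; no exception stated |
| 12.1.2 | haemoglobin, platelets, white-cell count and differential on four days; no exception stated |
| 9.7.1 to 9.7.3 | full blood count, or else differential, haematocrit and haemoglobin |
| Appendix 1 | haemoglobin and haematocrit only, where no full blood count is done |
| 9.10 | some sites cannot do the full blood count; number not given |

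Absolute neutrophil count = total white-cell count x neutrophil fraction. The alternative in 9.7 supplies the fraction but lists no total, so the absolute count cannot be formed unless the total is also measured. It lists no platelets. Under the Appendix 1 wording even the fraction is missing. Haemoglobin is obtained in every case.

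**4. Denominators.** The plan has 72 ACT and 144 TACT subjects per matching pair per site.

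- AL pair, 8 sites: 8 x 72 = 576 and 8 x 144 = 1152.
- ASMQ pair, 7 sites (Rwanda excluded): 7 x 72 = 504 and 7 x 144 = 1008.

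If k sites have no full blood count, the largest possible AL denominators for platelets are 576 - 72k and 1152 - 144k. The value of k is an assumption. Across k = 1 to 7 the range is wide:

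| k | ACT | TACT |
|---|---|---|
| 1 | 504 | 1008 |
| 2 | 432 | 864 |
| 6 | 144 | 288 |
| 7 | 72 | 144 |

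These are planned enrolments, before losses. The documents give no marrow-event rate, so no expected number of events and no power can be derived for these rows.

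**The case against.** The best defence is that the marrow is not left out of safety reporting, and much of it stands. Protocol 12.1.1 counts an abnormal laboratory result as an adverse event, 12.1.2 has abnormal counts graded and followed, and 12.1.3 gives blood dyscrasias as an example of a serious event. The list in SAP 3.4 marks emphasis and is not exclusive. SAP 3.4 also undertakes to describe clinically relevant abnormalities. A reader might infer that a case of agranulocytosis would go unreported; the documents do not support that. A detected case could enter the overall adverse-event or serious-event comparison. What is missing is a prespecified marrow comparison with its own denominator.

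Three other strong readings also fail:

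- **That no blood count is compared.** The haemoglobin row in Table 6 uses the same scheduled draws.
- **That the endpoint is unmeasured at sites without a full blood count.** Section 9.7 still yields haemoglobin and a neutrophil share there, and the documents do not say that those sites lack a total white-cell count; they only omit to list one.
- **That untested subjects will be counted as normal.** SAP 1.1 includes patients in safety analyses only where they have the data, and the laboratory rows of Table 6 are laid out as n/N. The denominator for these counts deserves to be explicit, but the plan does not direct the error.

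It is also fair to say that bradycardia is not named in the secondary endpoint. The mismatch between footnote and rows is a slip in the table shell, not a lost endpoint.

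**Conclusion.** The point holds in this limited form. One named component of the secondary safety endpoint has no planned comparison beyond haemoglobin: total white cells, neutrophils and platelets appear in neither the text of SAP 3.4 nor Table 6. The bradycardia row that the footnote presupposes is also absent. The protocol contradicts itself on whether platelets and white-cell counts exist for everyone: sections 7 and 12.1.2 say so without exception, section 9.7 allows a substitute, and Appendix 1 describes a lesser one.

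The size cannot be put as a number of missed events, because the documents give neither a marrow-event rate nor the number of sites without full blood counts. The protocol calls agranulocytosis rare and ties it to prophylactic use, so its general scenario of a rise from 1 in 100 to 3 in 100 should not be read as a marrow rate. The primary efficacy analysis is not affected. This should be settled before the analysis, and it is easy to settle.

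**What to change.** **SAP 3.4 and Table 6.** Add graded rows for total white-cell count, absolute neutrophil count and platelets, and the bradycardia row that the footnote already defines. Compare matching arms with the Fisher's exact test already named. For each parameter, use as denominator the subjects with a post-baseline result for it, and list the sites without full blood counts. State the bradycardia definition in the SAP, since the footnote gives only the counting rule. Name one grading scale for the new rows: Protocol 12.1.2 uses CTCAE and SAP 3.4 uses the DAIDS table.

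**Protocol.** Reconcile sections 7, 9.7.1 to 9.7.3, 12.1.2 and Appendix 1 on what is measured where no full blood count is done, including whether a total white-cell count is taken. The new text should keep clear that haemoglobin is collected either way.

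**Cost.** A few table rows, a sentence or two in the SAP and a protocol clarification; no new samples. The drawback is that the marrow-safety denominators will be visibly smaller than the full safety population, by an amount the documents do not give.

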4.2. Secondary objectives

- To compare the safety and tolerability of ACTs and TACTs within and across sites and regions, including comparisons of 'non-matching' ACTs vs TACTs (AL+PBO versus ASMQ+PPQ, ASMQ+PBO versus AL+AQ).
- To compare additional measures of treatment efficacy between treatment arms, including the 63-day ACPR, the post-treatment prophylactic effect of ACTs and TACTs defined as the 42-day and 63-day PCR uncorrected ACPR, gametocyte carriage, parasite clearance rates and fever clearance.
- To assess pharmacokinetic and pharmacodynamic interactions between antimalarials in TACTs

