9.5.5. Clinical procedures in case of a recurrent infection

- Standardized symptom questionnaire
- Physical examination

- Weight, height, pulse, blood pressure, respiratory rate
- Tympanic temperature
- Completion of recurrent infection form
- Treatment of recurrent infection.
- Recording of treatment for recurrent infection in the concomitant medication form

Subjects with persistent asexual parasitaemia on day 7 or who develop a recurrent parasitaemia after day 7 with no signs of severity will be treated with either the same or another ACT or a different combination e.g. quinine and doxycycline or clindamycin, in accordance with local recommendations.

Subjects who develop a non-falciparum parasitaemia during follow up will be treated according to local guidelines.

In case of a recurrent infection, subjects should still be followed up according to the study protocol until day 63. An additional questionnaire on the place of living, work and travel and mobile phone use in the period between the initial infection and the recurrent infection will be completed.

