12.1. Definitions

12.1.1. Adverse events (AEs)

An AE is any undesirable event or clinical deterioration that occurs to a study participant during the course of the study; that is, from the time of administration of study drugs until study ends (i.e., until the follow up visit) whether or not that event is considered related to the study drugs, or to a concomitant drug or procedure, e.g.:

- any unfavourable and unintended symptom
- physical sign
- abnormal laboratory result
- an illness
- any pre-existing condition that has worsened in grade

Any new clinical sign or clinical deterioration that occurs between signing the consent form and the administration of study drugs is not an AE. This information will be recorded in the medical records, as a pre-existing condition.

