## STATISTICAL ANALYSIS PLAN

**Table 6 Adverse events within the first 42 days**

Adverse events	AL+Placebo	AL+AQ	ASMQ+Placebo	ASMQ + PPQ
Number of subjects	XXXX	XXXX	XXXX	XXXX
Vomiting/number of treatments, n/N, (%)	XXX/XXXX (XX.X)	XXX/XXXX (XX.X)	XXX/XXXX (XX.X)	XXX/XXXX (XX.X)
Serious adverse events (SAEs), n/N, (%)	XX/XXXX (XX.X)	XX/XXXX (XX.X)	XX/XXXX (XX.X)	XX/XXXX (XX.X)
Possible, probable or definite drug related SAEs, n/N, (%)	XX/XXXX (XX.X)	XX/XXXX (XX.X)	XX/XXXX (XX.X)	XX/XXXX (XX.X)
QTc >500ms (H4 and H48/H52)	XXX/XXXX (XX.X)	XXX/XXXX (XX.X)	XXX/XXXX (XX.X)	XXX/XXXX (XX.X)
Change from baseline in haemoglobin at days 3, 7, 28 (stratified for G6PD status)	XXX/XXXX (XX.X)	XXX/XXXX (XX.X)	XXX/XXXX (XX.X)	XXX/XXXX (XX.X)
Grading of adverse events, n/N, (%)	1-2	3-4	1-2	3-4
Symptoms, n/N (%)	X/XX (X.X)	X/XX (X.X)	X/XX (X.X)	X/XX (X.X)
Headache	X/XX (X.X)	X/XX (X.X)	X/XX (X.X)	X/XX (X.X)
Fatigue	X/XX (X.X)	X/XX (X.X)	X/XX (X.X)	X/XX (X.X)
Abdominal pain	X/XX (X.X)	X/XX (X.X)	X/XX (X.X)	X/XX (X.X)
Loss of appetite	X/XX (X.X)	X/XX (X.X)	X/XX (X.X)	X/XX (X.X)
Nausea	X/XX (X.X)	X/XX (X.X)	X/XX (X.X)	X/XX (X.X)
Vomiting	X/XX (X.X)	X/XX (X.X)	X/XX (X.X)	X/XX (X.X)
Diarrhea	X/XX (X.X)	X/XX (X.X)	X/XX (X.X)	X/XX (X.X)
Itching	X/XX (X.X)	X/XX (X.X)	X/XX (X.X)	X/XX (X.X)
Dizziness	X/XX (X.X)	X/XX (X.X)	X/XX (X.X)	X/XX (X.X)
Blurred vision	X/XX (X.X)	X/XX (X.X)	X/XX (X.X)	X/XX (X.X)

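### The 42-day adverse event comparison does not separate events after a recurrent malaria episode, so the symptom rows, total SAEs and day-28 laboratory values can be diluted or biased

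*SAP*

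**What the plan says.** SAP 2.1.3 sets the safety endpoint as "Incidence of adverse events and serious adverse events within the first 42 days". SAP 3.4 restricts its summaries to treatment-emergent events, those being "adverse events that newly started or increased in intensity after the study drug administration". The method is "comparing the frequency (%) of adverse events and serious adverse events" with Fisher's exact test, by intention to treat. Table 6 is titled "Adverse events within the first 42 days". No end point at recurrence is given.

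Protocol 12.1.1 counts an event "whether or not that event is considered related to the study drugs, or to a concomitant drug or procedure", and its examples include an illness and an abnormal laboratory result. Under Protocol 9.5.5 a subject with recurrent parasitaemia "will be treated with either the same or another ACT or a different combination". The same section adds: "In case of a recurrent infection, subjects should still be followed up according to the study protocol until day 63". Protocol 11 says that recurrent parasitaemia is not a reason to discontinue.

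Protocol 4.2 makes prophylaxis a between-arm question. Among the measures to be compared is "the post-treatment prophylactic effect of ACTs and TACTs defined as the 42-day and 63-day PCR uncorrected ACPR".

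For efficacy, SAP 3.3 (handling of missing data) censors reinfections in the survival analysis or treats them as competing risks. SAP 3.4, Table 6 and Protocol 15.2.4 have no counterpart for safety.

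**The concern.** Headache, fatigue, abdominal pain, loss of appetite, nausea, vomiting and dizziness are Table 6 rows. Each can come from the study drugs, from a new malaria episode or from the drugs given to treat it. Under the plan all of these count for the randomised arm.

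There are two effects. Recurrences at the same rate in both arms add background events and reduce power. Recurrences at different rates also move the estimated difference, because the arm with fewer recurrences collects fewer malaria-related events. If the TACT protects longer, an excess due to the added partner drug would be understated.

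Safety and tolerability is the first secondary objective, and Protocol 15.1 gives more safety data on TACTs as the reason for the 1:2 allocation. SAP 3.4 gives particular attention to abdominal pain and appetite, two of the exposed rows.

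**Working it through.** **Inputs from the documents.** The design contrast is 1% (ACT) versus 3% (TACT) (Protocol 15.1, SAP 2.2.1). The AL pair pooled with Asia is 918 versus 1,494, and the ASMQ pair 789 versus 1,293 (Protocol 15.1). The Africa-only AL pair is 8 × 72 = 576 versus 8 × 144 = 1,152. The test is Fisher's exact (SAP 3.4).

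**Assumptions.** No significance level is stated for safety, so I use two-sided 5%. The documents give neither the day-42 recurrence rate by arm (rA for ACT, rT for TACT) nor the chance q that a recurrence or its re-treatment produces the event in question. I vary all three and take recurrence to be independent of the drug-related event.

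**The plan's own figure.** Exact Fisher power for 1% versus 3% with the Africa and Asia numbers is 92.5% (AL) and 88.0% (ASMQ), so the stated power of more than 80% reproduces. For Africa alone the AL pair gives about 78%. The shortfall against the stated 80% is a separate matter.

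**Observed rates.** ACT: pA = 1 − 0.99 × (1 − rA·q). TACT: pT = 1 − 0.97 × (1 − rT·q). For example, with rA = 0.20, rT = 0.10 and q = 0.20:
- pA = 1 − 0.99 × 0.96 = 4.96%
- pT = 1 − 0.97 × 0.98 = 4.94%

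Power to show the TACT worse, AL pair:

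| Recurrence ACT / TACT | q | Observed ACT / TACT | Difference (points) | Pooled with Asia | Africa only |
|---|---|---|---|---|---|
| none | – | 1.0% / 3.0% | +2.0 | 92% | 78% |
| 10% / 10% | 10% | 2.0% / 4.0% | +2.0 | 77% | 58% |
| 10% / 5% | 10% | 2.0% / 3.5% | +1.5 | 55% | 38% |
| 20% / 10% | 20% | 5.0% / 4.9% | 0.0 | 2% | 2% |
| 30% / 15% | 40% | 12.9% / 8.8% | −4.1 | 0% | 0% |

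In the last row the TACT would appear significantly safer in about 87% (pooled) or 72% (Africa only) of trials.

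**Separating the two effects.** With pooled numbers and q = 10%, equal recurrence of 10% takes power from 92% to 77%, which is noise alone. Moving to 10% versus 5% takes it from 77% to 55%, which is the differential part. So 15 of the 37 points lost are not bias.

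**Size of the bias itself.** With a common underlying event rate p, the difference shifts by (1 − p)(rA − rT)q. For small p the 2-point excess is cancelled when (rA − rT)q is about 0.02. For a common symptom with p = 18%, the AL vomiting rate in Protocol 19.4.1, the shift is 0.82 × 0.5 = 0.4 points at 10% versus 5% with q = 10%. It is 0.82 × 2.0 = 1.6 points at 20% versus 10% with q = 20%.

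**The case against.** **Counting is inferred.** No sentence says that symptoms of a recurrence are recorded as adverse events. The procedure list in Protocol 9.5.5 has a recurrent infection form but, unlike the lists for weekly and unscheduled visits, no line for recording adverse events. This stands as an ambiguity. The wide definition in 12.1.1, and the symptom questionnaire that Protocol 12 uses at every visit to find adverse events, still make counting the natural reading.

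**Much of the safety analysis is not exposed.** This stands. In-hospital QTc, vomiting and retreatment after dosing, course completion and day 3 and day 7 laboratory values precede almost all recurrences. Table 6 also has a drug-related row, but for SAEs only. Causality is graded for every event (Protocol 12.3.2), and Table 6 does not use it for non-serious ones. A reader might infer that the whole ACT-TACT safety comparison is compromised. The documents do not support that.

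**Direction and size are not known.** This also stands. A reader might infer that the TACT will look safer than it is. The documents predict no gap in recurrence; they only plan to look for one. The rates in the table are assumed. The 1% versus 3% contrast is for rare events, whereas Protocol 19.4.1 puts several symptom rows far above 1%, so the power figures do not transfer to those rows.

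**The 42-day intention-to-treat count is a legitimate choice.** It measures total burden, including malaria averted. That is a reason to keep it. It does not tell the reader what the added drug does.

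**Conclusion.** The point holds for the non-serious symptom rows, total SAEs and day-28 haemoglobin and biochemistry. These pool drug effects with the effects of later malaria episodes and their treatment, in a trial that is itself asking whether the rate of such episodes differs by arm.

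The loss could be modest or complete. For a 1% versus 3% event in the pooled AL pair, power of about 92% falls to about 55% in a moderate scenario and to about 2% in a heavier one. Part of the moderate loss is noise that equal recurrence would also cause. These figures rest on assumed recurrence and symptom rates, on recurrence being lower under the TACT, and on recurrence symptoms being recorded as adverse events. If the arms have equal recurrence, dilution remains but the difference hardly moves. If recurrence is lower under the ACT, the bias runs the other way.

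This is an inexpensive improvement to the SAP. It does not invalidate the safety analysis.

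**What to change.** In SAP 3.4 and Table 6, before any unblinded comparison:

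- Keep the 42-day all-event table.
- Beside it, pre-specify an ACT-TACT comparison of events with onset before the subject's first recurrent parasitaemia or first non-study antimalarial. Report it as cumulative incidence with recurrence as a competing event, or per person-time.
- Smears in follow-up are weekly or prompted by symptoms, so symptoms usually start before the recurrence is detected. Assign symptoms first reported at the detection visit to the recurrence.
- Show events by period: to day 7, and after day 7.
- Add a drug-related row for all adverse events, using the causality grades already collected.
- Report day-28 haemoglobin and biochemistry with and without subjects who had a recurrence by then.
- State whether symptoms of a recurrence are recorded as adverse events.

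**Cost.** SAP text, some extra tables and somewhat less person-time after day 7. Visits, treatment and sample size do not change. Recurrences and their treatment are already recorded on forms (Protocol 9.5.5). The documents do not say that event onset dates are captured, so the case report form should be checked. The new comparison conditions on a post-randomisation event that may itself depend on treatment, which is why the 42-day table stays.
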